The PK parameters of plasma BN101 in the subjects are shown in Table 2. BN101 was rapidly absorbed after a single oral dose, peaking at a median of 1.5 hours (range: 0.5-2.0 hours); the elimination half-life was highly variable, with a median elimination half-life of 10.35 hours and 8.92 hours at the 200 mg dose and 400 mg dose, respectively. Overall, the AUC₀₋₂₄ of BN101 increased slightly with dose, but was lower than dose proportionality, with a mean AUC₀₋₂₄ of 9040.44 ng*h/mL at the 200 mg dose and 9984.00 ng*h/mL at the 400 mg dose, respectively. The C_{max} was similar in the

2 dose cohorts, with a mean C_{max} of 2355.02 ng*h/mL at the 200 mg dose and 2355.02 ng*h/mL at the 400 mg dose, respectively.

Table 2 Plasma BN101/belumosudil pharmacokinetic parameters-PK analysis set

Trantmant	_	PK Parameters				
Treatment group	Statistic	AUC_{0-24}	$\mathrm{AUC}_{0\text{-}\infty}$	C_{max}	$T_{1/2}$	T_{max}
		(ng*h/mL)	(ng*h/mL)	(ng/mL)	(h)	(h)
BN101 200mg (N=8)	Median	6883.41	7635.11	2204.59	10.35	1.50
	Minimum	4057.36	4490.96	976.96	2.13	0.5
	Maximum	18074.16	19561.24	4265.25	48.01	2.0
	Arithmetic mean	9040.44	10055.32	2355.02	14.28	/
	Coefficient of variation	58.64	59.39	45.53	103.52	/
BN101 400mg (N=9)	Median	8120.87	10264.37	2181.44	8.92	1.50
	Minimum	4426.67	4837.27	941.48	3.85	0.5
	Maximum	19691.89	20375.86	3939.14	28.69	2.0
	Arithmetic mean	9984.00	10981.49	2315.84	11.80	/
	Coefficient of variation	56.21	51.12	48.25	69.22	/

N is the number of subjects entering the analysis set in each group.

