- 7) Study drug administration;
- 8) Issuance/retrieval of subject logs;
- 9) Combined medications/treatments (including doses of corticosteroids and other cGVHD treatments);
- 10) AE.

It is up to the investigator to decide whether or not to perform this test based on the subject's condition.

4.3.3 Day 1 of Cycle 2 ~ Cycle N (C2D1 ~ CxD1, time window for the corresponding examination: ±3 days):

Prior to dosing

- 1) Co-medication/treatment (including doses of corticosteroids and other cGVHD treatments);
- 2) AE
- 3) Symptom-directed physical examination;
- 4) Vital signs (including temperature, respiratory rate, sitting blood pressure and pulse);

- 5) Body weight;
- 6) ECOG PS score;
- 7) Blood routine, urine, and blood biochemistry;
- 8) 12-lead electrocardiogram (3 consecutive measurements taken within 60 minutes prior to dosing on Day 1 of Cycle 2 and Cycle 4, each 1 to 2 minutes apart);
- 9) Echocardiogram (LVEF)#;
- 10) Urine pregnancy test (for females of childbearing age only, positive results to be confirmed by serologic testing);
- 11) PK blood collection (within 60 minutes prior to dosing on Cycle 2, Cycle 3 and Cycle 4 Day 1);
- 12) Physician cGVHD activity assessment[†];
- 13) cGVHD response assessment[†];
- 14) Pulmonary function tests† [may also be assessed post-dose; where a complete pulmonary function test including FEV1, FVC, DLCO (corrected for Hb), TLC, and RV is required on Day 1 of Cycle 4, Cycle 7, and every 6 cycles thereafter (e.g., Cycle 13, Cycle 19, as applicable), and on other cycles (e.g., Cycle 2, Cycle 3, Cycle 5, and Cycle 6, etc.), a spirometer test only (including FEV1 and FVC testing) is required];
- 15) Patient-reported cGVHD activity assessment[†];
- 16) Lee Symptom Scale score[†];
- 17) PROMIS Physical-Psychological Functioning Global Health Score[†].
- # The decision to perform this test was made by the investigator on a subject-by-subject basis.

Drug administration and post administration

- 1) Administration of study drug;
- 2) Dispensing/recovery of study drug and subject logs;
- 3) Combined medications/treatments (including doses of corticosteroids and other cGVHD treatments);
- 4) AE;
- 5) 12-lead electrocardiogram [3 consecutive measurements 1.5 hours (± 20 minutes) after dosing on Day 1 of Cycle 2 and Cycle 4 at 1-2 minute intervals; single measurement 1.5 hours (± 20 minutes) after dosing on Cycle 7 and subsequent visits];

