- 9. Virology includes Hepatitis B Surface antigen (HBsAg), Hepatitis B Surface Antibody (HBsAb), Hepatitis B core antibody (HBcAb), Hepatitis Be antigen (HBeAg), Hepatitis Be antibody (HBeAb), Hepatitis C antibody (HCV-Ab), human immunodeficiency virus (HIV) antibody, Hepatitis B virus DNA (HBV-DNA) (if applicable), Hepatitis C virus RNA (HCV-RNA) (if applicable). If they are done at the site within 28 days prior to screening and reports can be provided, the investigator determines that the test can be used as a result of the screening period. When HBcAb or HCV-Ab is positive, HBV-DNA or HCV-RNA should be tested to rule out active infection.
- 10. 12-Lead ECG see ECG Assessment table.
- 11. Female of childbearing age are tested for pregnancy. For this study, the reproductive age was defined as non-menopausal, and menopause included natural amenorrhea ≥12 months; Or natural amenorrhea ≥24 months after chemotherapy; Or natural amenorrhea ≥6 months and serum follicle-stimulating hormone (FSH) level > 40 IU/L; Or confirmed surgical records and/or pathology reports confirmed after bilateral oophorectomy. Serum pregnancy tests for women of childbearing age during the screening period must be negative. Urine pregnancy test can be performed as needed during the study treatment. Positive results are to be confirmed with serum testing. If the urine pregnancy result is positive, subjects should stop the study drug treatment and withdraw from the study, and the investigators will continue to follow up subjects until delivery and 30 days after delivery. Subjects who did not deliver were followed up until the end of the pregnancy.
- 12. On Day 1 of Cycles 1 to 7, subjects will take their dose at the clinic and then will be dispensed study drug for home administration. Instruct subjects to fill in the study drug dairy. From Cycle 8 onwards, the Day 1 dose may be taken at home or in the clinic.

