- 13. The end of the main study is defined as 12 months after the last subject was enrolled. Subjects who have not yet experienced cGVHD progression at the end of the main study, and in the judgment of the investigator, the benefits of continued dosing outweigh the risks, may submit a written request and, upon approval by the sponsor's Medical Director and documentation of the subject's willingness to continue the treatment, the sponsor will continue to provide BN101/belumosudil medication at no cost until cGVHD progression, intolerable toxicity, initiation of a new cGVHD therapy, recurrence of hematological neoplasm, loss to follow-up, withdrawal of consent, or death, etc., whichever occurred first. For subjects assessed as "Lack of Response Mixed" and "Lack of Response Progression" (see the main body of the protocol), if the investigator believed that these subjects could continue to benefit from treatment with BN101/belumosudil, the treatment may be continued after a written application was submitted, and approval from the Sponsor's Medical Director as well as documentation of the subject's willingness to continue treatment was obtained.
- 14. On the first day of cycle 7 (C7D1) and all subsequent odd cycles (C7D1, C9D1, C11D1, etc.), subjects will receive 2 cycles of study drugs and 2 copies of drug dairy and return to the clinic for efficacy and safety assessment every other treatment cycle, as well as dispense/collect study drugs until the end of the main study.
- 15. Subjects will return to the clinic for EOT assessment within 7 days after the final administration of the study drug or at the end of the main study (only for subjects who have not discontinued the study drug at the end of the main study). Subjects who withdraw from the trial early should also return to the clinic for EOT assessment. End-of-treatment visits are also required at the end of the main study if subjects have not discontinued study drug at the end of the main study. EOT

Cycle Day (d)	Screening/Baseline		Cycle 1		Cycle 2~N ^{13,14}	End of Treatment (EOT) ¹⁵	28-Day Follow-Up ¹⁶	Long Term Follow-Up ¹⁷
Assessment	-14 ~ -1	-7 ~ -1	C1D1	C1D8、15 (±3)	CxD1 (±3)	(+7)	(土)	At the end of treatment or at the end of the main study

visits should be done prior to new treatment.

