Appendix 4 ECG Assessments

ECG Assessments		
Cycle 1	Day 1	Triplicate ECG within 60 minutes prior to
		BN101/belumosudil dosing and at 1.5 hours post dose (\pm 20
		minutes), they should be taken at 1-2 minutes intervals
Cycle 2	Day 1	Triplicate ECG within 60 minutes prior to
		BN101/belumosudil dosing and at 1.5 hours post dose (\pm 20
		minutes), they should be taken at 1-2 minutes intervals
Cycle 4	Day 1	Triplicate ECG within 60 minutes prior to
		BN101/belumosudil dosing and at 1.5 hours post dose (\pm 20
		minutes), they should be taken at 1-2 minutes intervals
Cycle 7 and every 2 cycles	Day 1	Single ECG at 1.5 hours post dose (± 20 minutes)
thereafter (only until the end of the		
main study)		
ЕОТ		Single ECG
28-Day Follow-up (only until the		Single ECG
end of the main study)		

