8.5.2. Laboratory Evaluations

The summary statistics of all hematology and biochemistry variables and change from baseline will be presented for each study assessment.

For shift tables, laboratory results will be classified using the CTCAE V5.0. All graded laboratory parameters will be summarized separately for hematology and biochemistry. Corresponding shift tables to compare baseline to the worst post-baseline grade within the treatment period will be provided.

For parameters of hematology and biochemistry, plots of mean / mean change from baseline with the corresponding standard error will be displayed.

Subject listing for hematology, biochemistry and urinalysis will be provided.

8.5.3. 12 Lead ECG

Descriptive statistics for ECG parameters at each time point will be presented for the values and change from baseline.

The number and percentage of patients with observed QTcF values that satisfy the following conditions will be presented by study visit. The number and percentage of patients with longest QTcF values that satisfy the following conditions will be summarized.

- ≤ 450 msec
- >450 to ≤ 480 msec
- >480 to ≤ 500 msec
- >500 msec

The number and percentage of patients having change from baseline QTcF values that satisfy the following conditions will be presented by study visit. The number and percentage of patients with longest change from baseline QTcF values that satisfy the following conditions will be summarized.

- ≤ 0 msec
- >0 to ≤ 30 msec
- >30 to ≤ 60 msec
- > 60 msec

Subject listing for ECG results will be provided.

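### From Cycle 9 the protocol requires an ECG 1.5 h ± 20 min after a dose that may be taken at home, so its timing is neither assured nor shown to be verifiable, and pre-dose items at the same visits conflict with a home dose

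*Protocol*

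**What the plan says.** Appendix 1, note 12, sets the place of dosing in two steps. Up to Cycle 7 it is fixed: "On Day 1 of Cycles 1 to 7, subjects will take their dose at the clinic". After that it is open: "From Cycle 8 onwards, the Day 1 dose may be taken at home or in the clinic".

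The ECG schedule does not change at the same point. Section 4.3.3 asks for a "single measurement 1.5 hours (± 20 minutes) after dosing on Cycle 7 and subsequent visits", and Appendix 4 gives the same timing for Cycle 7 and every second cycle after it, until the end of the main study. Note 14 of Appendix 1 has patients "return to the clinic for efficacy and safety assessment every other treatment cycle" from C7, so the ECG days after C7 are C9, C11, C13 and so on, and the patient attends the clinic on each of them.

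Section 4.3.3 also lists items to be completed before dosing at these visits, among them blood and urine tests. Section 8.4 says that laboratory samples are to be taken before the dose. Neither makes an exception for Cycle 8 onwards.

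SAP 8.5.3 then uses the ECGs in two ways. One is by visit: "The number and percentage of patients with observed QTcF values that satisfy the following conditions will be presented by study visit", with a matching table for change from baseline. The other takes each patient's longest QTcF and longest change from baseline. Neither refers to time since dose.

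**The concern.** A dose-timed ECG needs a known dose time and a patient who is at the machine when the window opens. Up to C7 the clinic dose supplies both. From C9 the protocol keeps the window but no longer requires the clinic dose, and no other rule fills the gap.

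The ±20 minute tolerance shows that timing was meant to matter. The nominal 1.5 h equals the median Tmax in the Chinese healthy-volunteer study (section 1.5, Table 2). From C7 there is only one scheduled ECG per visit and no pre-dose ECG, so an off-window reading leaves that visit with no dose-timed ECG at all.

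QTcF is a named safety endpoint (section 7.2), and safety is part of the primary objective. If readings from C9 onwards come from different times after the dose and the tables do not show it, an unremarkable row is hard to interpret: a QT effect near the peak that appears late could have been missed.

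**Working it through.** No design figure is involved. The check is a cross-reading of the passages plus a count of visits.

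**1. The window.** 90 min ± 20 min = 70 to 110 min post-dose, 40 min wide.

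**2. The rules on an odd-cycle Day 1 from C9.**

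| Requirement | Source | Dose in clinic | Dose at home before the visit | Dose at home after the visit |
|---|---|---|---|---|
| Pre-dose assessments and samples | 4.3.3, 8.4 | Can be met | Cannot be met as specified | Can be met |
| ECG 70 to 110 min post-dose | Appendix 4, 4.3.3 | Can be met | Only if arrival happens to fit | Cannot be met at that visit |

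A clinic dose satisfies every passage. No home dose satisfies both rows.

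**3. Is the gap closed elsewhere?** Section 4.4.1 requires dosing at the centre on PK sampling days, but scheduled PK sampling ends at C4 (Appendix 2). Nothing in the protocol or SAP tells a home-dosed patient when to arrive, says that the clock time of a home dose is recorded, or says what to do with an ECG outside the window. A drug diary is kept, but its fields are not shown.

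**4. Which visits, and how many?** With 28-day cycles, the nominal day of CnD1 is 28 × (n − 1) + 1.

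| Visit | Calculation | Nominal day |
|---|---|---|
| C7 (clinic dose required) | 28 × 6 + 1 | 169 |
| C9 | 28 × 8 + 1 | 225 |
| C11 | 28 × 10 + 1 | 281 |
| C13 | 28 × 12 + 1 | 337 |
| C15 | 28 × 14 + 1 | 393 |
| C17 | 28 × 16 + 1 | 449 |
| C19 | 28 × 18 + 1 | 505 |
| C21 | 28 × 20 + 1 | 561 |

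- Last-enrolled patient, treated for the full 12 months to the end of the main study (365 days): C9, C11 and C13 are exposed, since C15 falls on day 393. That is 3 of the 4 timed ECG visits after C4.
- First-enrolled patient, with the 6-month accrual estimated in SAP section 4, treated for about 18 months (548 days): C9 to C19 are exposed, since C21 falls on day 561. That is 6 of the 7 timed ECG visits after C4.
- At a data lock 6 months after the last enrolment (section 3.5): none for the last-enrolled patient (about day 183, before C9), and up to 3 for the first-enrolled (about day 365).

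**5. What is unaffected?** C1, C2 and C4 have triplicate ECGs before and after a clinic dose, and C7 has a single post-dose ECG after a clinic dose.

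**6. Effect on the SAP summaries.** The by-visit tables keep C9 and later in their own rows, so mixing of in-window and off-window readings can occur only within those rows. The longest value is a maximum, so adding an off-window ECG cannot lower it. What can be lost is a high reading that an in-window ECG at C9 or later would have caught.

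**The case against.** The best defence is that the schedule can be followed. Home dosing is optional, the patient attends the clinic on every ECG day, and section 4.3.3 sets out the visit in order: pre-dose items, administration of study drug, then the timed ECG. On this reading the home option serves the even cycles, which have no visit from C8. Deviations must also be documented (section 11.7) and classified before lock (SAP 5.4), and no decision rule depends on ECGs at C9 or later.

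Much of this stands, and it limits the size of the point. It does not remove the conflict. Note 12 makes no distinction between odd and even cycles, and its mention of the clinic has practical meaning only on visit days, so a site that lets a patient dose at home on C9D1 is following the protocol as written. A deviation log does not put time since dose into the QTcF tables.

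A reader might go further and infer that peak-exposure QTcF monitoring fails at these visits, or that late QTcF is biased towards no effect. The documents do not support either. They give no travel or arrival times, and some home doses could still fall within the window. Nor are these ECGs the only evidence under continued dosing: C7 falls on nominal day 169 after a required clinic dose, and there is an untimed ECG at end of treatment.

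The peak itself is also less certain than 1.5 h suggests. That figure comes from single doses in 8 and 9 healthy volunteers, while section 1.4.1 gives 1 to 6 h across the overseas studies. For the same reason Table 2 cannot be used to say how far exposure has fallen by the time of a late ECG. Mean AUC0-24 divided by 24 h is 9040.44/24 = 377 ng/mL, about 16% of the mean Cmax of 2355.02 ng/mL, but this is a whole-day average and does not describe a reading a few hours after the dose.

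**Conclusion.** The inconsistency is real and should be corrected. As written, a patient may dose at home on a day when the protocol requires a post-dose ECG within a 40-minute window and also requires pre-dose samples and assessments. For such patients the ECG timing is neither assured nor shown to be verifiable, and the pre-dose items cannot be done as specified when the dose comes before the visit. The by-visit QTcF rows from C9 could then combine in-window and off-window readings without this being visible, and a late peak effect could be missed.

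The counts of 3 and 6 exposed visits are upper limits. They assume 28-day cycles without delay, 6 months of accrual, uninterrupted treatment and home dosing on each of those days; how many patients would dose at home cannot be derived from the documents. The QTcF evidence from C1, C2, C4 and C7 is untouched, and no patient's longest QTcF can be lowered by an off-window reading.

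**What to change.** 1. Reconcile Appendix 1 note 12 with Appendix 4 and sections 4.3.3 and 8.4, so that place of dosing, ECG timing and pre-dose items agree at C9 and later. How to do so is for the sponsor to decide.
2. Record the clock time of the dose and of the ECG on every ECG day.
3. In SAP 8.5.3, use in-window post-dose ECGs for the post-dose entries of the by-visit QTcF tables, and list off-window ECGs separately with time since dose. Keep all ECGs in the longest-QTcF and longest-change summaries; this fits SAP 8.1, which lets unscheduled measurements count towards worst-case values.

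The cost is a schedule correction, one extra data field and a little more analysis work. Dose times that were never recorded cannot be recovered reliably after database lock, so the data field is the urgent part.

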Appendix 2 Pharmacokinetics Sampling

PK Sample Collection					
Sample	Blood (appr	coximately 3 mL every time point), separated plasma			
Extensive blood sampling: 12 su	bjects at seld	ected sites			
Cycle 1	Day 1	Prior to BN101/belumosudil dosing, and at 1, 1.5, 2, 3, 4,			
		6, 8, 12 hours post dose			
	Day 2	Prior to BN101/belumosudil dosing			
	Day 15	Prior to BN101/belumosudil dosing			
Cycle 2 (or when withdrawing	Day 1	Prior to BN101/belumosudil dosing, and at 1, 1.5, 2, 3,			
from the study early)		4, 6, 8, 12 hours post dose			
	Day 2	Prior to BN101/belumosudil dosing			
Cycle 3 (or when withdrawing	Day 1	Prior to BN101/belumosudil dosing			
from the study early)					
Sparse PK: All Subjects					
Cycle 2 (or when withdrawing	Day 1	Prior to BN101/belumosudil dosing, and at 1.5, 4 hours post			
from the study early, except for		dose			
those who were in the extensive					
blood sampling group)					
Cycle 4 (or when withdrawing	Day 1	Prior to BN101/belumosudil dosing, and at 1.5, 4 hours post			
from the study early)		dose			

Appendix 3 Pharmacokinetic Blood Sample Collection Time Window

PK Time point	Time Window	
	Extensive blood sampling	Sparse blood sampling
Prior to BN101/belumosudil	-60 minutes to BN101/belumosudil	-60 minutes to BN101/belumosudil
	dose	dose
1、1.5、2、3 hours post dose	± 10 minutes	± 10 minutes
4, 6, 8 hours post dose	± 15 minutes	NA
12 hours post dose	± 60 minutes	NA
Note: NA = not applicable		

Appendix 4 ECG Assessments

ECG Assessments		
Cycle 1	Day 1	Triplicate ECG within 60 minutes prior to
		BN101/belumosudil dosing and at 1.5 hours post dose (\pm 20
		minutes), they should be taken at 1-2 minutes intervals
Cycle 2	Day 1	Triplicate ECG within 60 minutes prior to
		BN101/belumosudil dosing and at 1.5 hours post dose (\pm 20
		minutes), they should be taken at 1-2 minutes intervals
Cycle 4	Day 1	Triplicate ECG within 60 minutes prior to
		BN101/belumosudil dosing and at 1.5 hours post dose (\pm 20
		minutes), they should be taken at 1-2 minutes intervals
Cycle 7 and every 2 cycles	Day 1	Single ECG at 1.5 hours post dose (± 20 minutes)
thereafter (only until the end of the		
main study)		
ЕОТ		Single ECG
28-Day Follow-up (only until the		Single ECG
end of the main study)		

Appendix 5 cGVHD Activity Assessment for Clinician

	Score 0	Score 1	Score 2	Score 3				
Esophagus	No esophageal symptoms	Occasional dysphagia or odynophagia with solid food or pills during the past week	Intermittent dysphagia or odynophagia with solid and pills, but not for liquids or soft foods, during the past week	Dysphagia or odynophagia for almost				
☐ Abnormality present but explained entirely by non-GVHD documented cause (specify):								
□Abnormali	ty thought to represe	nt GVHD PLUS other caus	es (specify):					

	Score 0	Score 1	Score 2	Score 3
Upper GI	No symptoms	Mild, occasional symptoms, with little reduction in oral intake during the past week	Moderate, intermittent symptoms, with some reduction in oral intake during the past week	More severe or persistent symptoms throughout the day, with marked reduction in oral intake, on almost every day of the past week

\sqcup Abnormality present b	out explained	entirely by	y non-GVHD	documented	l cause ((specify	7):
--------------------------------	---------------	-------------	------------	------------	-----------	----------	-----

[☐] Abnormality thought to represent GVHD PLUS other causes (specify):

	Score 0	Score 1	Score 2	Score 3
Lower GI	No loose or liquid stools during the past week	Occasional loose or liquid stools, on some days during the past week	Intermittent loose or liquid stools throughout the day, on almost every day of the past week, without requiring intervention to prevent or	Voluminous diarrhea on almost every day of the past week, requiring intervention to prevent or correct

				correct volu	me depletion	volu	ıme depletion
□Abnormali	ty present but explai	ned entirely by non-C	GVHD	documented	cause (specify):		
□Abnormali	ty thought to represe	ent GVHD PLUS othe	er caus	ses (specify):			
	Score 0	Score 1		So	core 2		Score 3
	No symptoms	Mild symptoms (shortness of breath after climbing one f of steps)		Moderate sy (shortness o after walkin ground)	f breath	Severe symptoms (shortness of breath at rest; requiring O ₂)	
Lungs							
8	Spirometry	FEV ₁		FEV ₁	FVC		FVC
	Not done □	(% Predicted):		(L):	(%		(L):
					Predicted):		
□Abnormali	ty present but explai	ned entirely by non-C	SVHD	documented	cause (specify):		
□Abnormali	ty thought to represe	ent GVHD PLUS othe	er caus	ses (specify):			
	Score 0	Score 1		Sc	core 2		Score 3
Eyes	No symptoms	Mild dry eye symptoms not affecting ADL (requirement of lubricant eye drops ≤ 3 x per day)		lubricant ey		Severe dry eye symptoms significantly affecting ADL (special eyeware to relieve pain) OR unable to work because of ocular symptoms OR loss of vision due to KCS	
	-	ned entirely by non-C			cause (specify):		
□Abnormali	ty thought to represe	ent GVHD PLUS othe	er caus	ses (specify):			

	Score 0	Score 1	Score 2	Score 3
Joints And Fascia	No symptoms	Mild tightness of arms or legs, normal or mild decreased range of motion (ROM) AND not affecting ADL	Tightness of arms or legs OR joint contractures, erythema thought due to fasciitis, moderate decrease ROM AND mild to moderate limitation of ADL	significant decrease of ROM AND significant limitation of ADL

☐ Abnormality present but explained	l entirely by non-GVHD	documented cause	(specify):
-------------------------------------	------------------------	------------------	------------

 \Box Abnormality thought to represent GVHD PLUS other causes (specify):

		1 (Worst)	2	3	4	5	6	7 (Normal)	Score
	Shoulder	1	1	TT		* e		8	Not done □
		1 (Worst)	2	3	4	5	6	7 (Normal)	Score
P-ROM	Elbow	6	6	6	F	V	~		Not done □
Score		1 (Worst)	2	3	4	5	6	7 (Normal)	Score
	Wrist/finger	0	V		MA		1	**	Not done □
		1 (Worst)	2	3	4 (Normal)				Score
	Ankle	13	2	J	A				Not done □

\square Abnormality	present	but exp	lained	entirely	y t	oy non-GVHD d	locumented	l cause (sp	ecify)

☐ Abnormality thought to represent GVHD PLUS other causes (sp	ecity)):
---	--------	----

	Score 0	Score 1	Score 2	Score 3	
Skin	No BSA involved	1-18% BSA	19-50% BSA	>50% BSA	

□Abnormali	ty present but e	explained	entir	ely by non-GVHD	docı	umented	cause (sp	ecify	y):			
□Abnormali	ty thought to re	epresent (6VH	D PLUS other caus	ses (s	pecify):						
	Score 0			Score 1		So	ore 2			Sco	re 3	
Skin Features Score	No scler features	rotic			feat	perficial tures "n le to pino	ot hidel	clerot		Check all to Deep features "He (unable to Impaired Ulceration	scler idebou pinch) d mobi	otic
If skin feature	es score=3, BSA	A% of no	n-mo	oveable sclerosis/fa	sciiti	is:						
Other skin G	VHD features (scored by	BSA	A)								
	oular rash/erythous-like feature		\Box F	clerotic features Papulosquamous le Phyosis	sions	or	□Kera	tosis	pila	nris-like		
-		-	is pa	tient's skin and/or	_	tightenii	ng on the	follo	owir	ng scale, wh	ere 0 i	S
O Symptoms not at all severe	1 2	3	4	5	6		7	8		9	Mo seve symj ma possa	est ere pto
Mouth	Erythema	None	0	Mild or moderate erythema (<25%)	1	(≥2 Severe	oderate 5%) or erythem 25%)	a	2	Severe erythen (≥25%	na	3
	Lichenoid	None	0	Lichen-like	1	Lich	en-like		2	Lichen-l	ike	3

				changes (<25%)		changes (25%~50%)		changes (>50%)					
	Ulcers	None	0	(~2370)		Ulcers involving (≤20%)	3	Severe ulcerations (>20%)	6				
	Total score for all mucosal changes												
☐ Abnormality present but explained entirely by non-GVHD documented cause (specify):													
□ Abnormality thought to represent GVHD PLUS other causes (specify):													
	Total serum bilirubin ALT ALP												
Liver labs	(mg/dL)			(U/L)		(U/L)					
□Abnormali	ty present but	explained	entir	ely by non-GVHD	docu	mented cause (spec	ify):						
□Abnormali	ty thought to 1	epresent (GVH	D PLUS other caus	ses (s _l	necify):							
Global severi	ty rating												
	ere would you rate the severity of this patient's chronic GVHD symptoms on the following scale, where 0 is VHD symptoms that are not at all severe and 10 is the most severe cGVHD symptoms possible:												
0	1 2	3		4 5		6 7	8	9 10)				
Not at all severe								Mo seve					

Additional cGVHD details per organ

Lungs	Pulmonary Tests (PFT)		mon (single b	capacity for carbon oxide (DL_{CO}) reath, adjusted for emoglobin)		esidual Volume (RV) (L)		ng capacity C) (L)				
OTHER S	SKIN GVHI	D FEATUR	ES (NOT se	cored by BSA)								
Check all	that apply:											
□Hyperpi	gmentation		□Poikilod	erma		□Hair Invol	vement					
□Нурорія	gmentation		☐ Severe o	r generalized pruri	tus	□Nail Invol	vement					
	Keratoconj	unctivitis										
Eyes	sicca (KCS confirmed ophthalmo	by	□Yes			Io	□Not examined					
OTHER	Other indicators, clinical features or complications related to chronic GVHD [check all that apply and assign a score to severity (0-3) based on functional impact where applicable; none: 0; mild: 1; moderate: 2; severe: 3]											
cGVHD	□Ascites ((serositis) _		☐ Myasthenia Gravis								
FEATU	□Pericard	ial Effusion	·		$\Box P$	eripheral Neuropa	thy					
RES	□Pleural I	Effusion			$\Box P$	olymyositis	_					
	□Nephrot	ic syndrome	:		\Box C	others (specify):						
	Since starti	ing BN101/	belumosudil	, would you say tha	at this pa	atient's cGvHD is:						
_a CVIID	-3	-2	-1	0	1	2	3	Score				
cGVHD Status	Very much	Moderat ely	A little		A little	Moderately	Very much					
	worse	worse	worse	Same	better	better	better					

